Appendix A
ALS Functional Rating Scale – Revised¹
ALSFRS-R
 (ALS Functional Rating Scale)

** Please circle the number of your answer

Patient Name _____ MRN# _____ Date _____

1. Speech 4 normal speech processes 3 detectable speech disturbance 2 intelligible with repeating 1 speech combined with non-vocal communication 0 loss of useful speech	7. Turning in bed and adjusting bed clothes 4 normal 3 somewhat slow or clumsy, needs no help 2 can turn alone or adjust sheets with great difficulty 1 can initiate, cannot turn or adjust sheets 0 helpless
2. Salivation 4 normal 3 slight but definite excess of saliva in mouth, may have nighttime drooling 2 moderately excessive saliva, may have minimal drooling 1 marked excess of saliva with some drooling 0 marked drooling, requires constant tissue	8. Walking 4 normal 3 early ambulation difficulties 2 walks with assistance 1 non-ambulatory functional movement only 0 no purposeful leg movement
3. Swallowing 4 normal eating habits 3 early eating problems, occasional choking 2 dietary consistency changes 1 needs supplemental tube feedings 0 NPO (exclusively parenteral or enteral feedings)	9. Climbing Stairs 4 normal 3 slow 2 mild unsteadiness or fatigue 1 needs assistance 0 cannot do
4. Handwriting 4 normal 3 slow or sloppy, all words legible 2 not all words legible 1 able to grip pen, unable to write 0 unable to grip pen	R-1. Dyspnea (difficult or labored breathing; breathlessness or shortness of breath) 4 none 3 occurs when walking 2 occurs with one or more: eating, bathing, dressing 1 occurs at rest, either sitting or lying 0 significant difficulty, considering mechanical support
5a. Cutting food and handling utensils (patients without gastrostomy) 4 normal 3 somewhat slow and clumsy, needs no help 2 can cut most foods, slow or clumsy, some help needed 1 foods cut by someone else, can still feed slowly 0 needs to be fed	R-2. Orthopnea (difficult or labored breathing that occurs when laying flat and is relieved by elevating the head and chest with two pillows) 4 normal 3 some difficulty sleeping, d/t shortness of breath, does not routinely use more than two pillows 2 needs extra pillows to sleep (>2) 1 can only sleep sitting up 0 unable to sleep
5b. Cutting food and handling utensils (patients with gastrostomy) 4 normal 3 clumsy, able to perform manipulations 2 some help needed with closures and fasteners 1 provides minimal assistance to caregiver 0 unable to perform any aspect of task	R-3. Respiratory Insufficiency 4 none 3 intermittent use of BiPAP 2 continuous use of BiPAP at night 1 continuous use of BiPAP day and night 0 invasive mechanical ventilation by intubation/trach
6. Dressing and hygiene 4 normal 3 independent self care with effort or decreased efficiency 2 intermittent assistance or substitute methods 1 needs attendant for self care 0 total dependence	Total Score _____ / 48

¹ Cedarbaum JM, Stambler N, Malta E, et al. The ALSFRS-R: A revised ALS functional rating scale that incorporates assessments of respiratory function. BDNF ALS Study Group (Phase III). J Neurol Sci 1999; 169(1-2): 13–21

[figure not shown]
CONFIDENTIAL INFORMATION

The information in this study protocol is confidential. Any disclosure, copying or distribution of the information contained within is strictly prohibited without written consent from MonoSol Rx LLC.

APPENDIX B

Placement Diagram and Instructions for Use Riluzole Oral Soluble Film

Placement Diagram

Placement on the top surface
(Dorsal Aspect of the
Tongue):

Riluzole Oral Soluble film is to be centered on the top surface of the tongue, along the midline, with the posterior edge of the film along the posterior edge of the tongue as illustrated by the Figure.

Ensure film is completely adhered to the lingual surface.

Note: Figure is for illustrative purposes and not drawn to scale.

Figure: Placement of ROSF 50 mg on the top surface (dorsal aspect) of the tongue.

Instructions for Use:

1. Keep the Riluzole Oral Soluble Film in the foil pouch until ready for use and use it right way after it is taken out of the pouch.
2. Make sure your hands are dry.
3. Fold the pouch along the dotted line to expose the tear notch. Tear or cut with scissors.
4. Put the Riluzole Oral Soluble Film on the center of the top surface of the tongue immediately after taking it out of the pouch and close the mouth. It will dissolve in minutes. Administration with liquid is not necessary.
5. While the film is dissolving do not chew, talk, swallow the film, or move the film from placement.
6. As the film dissolves swallow your saliva in the normal manner.

CONFIDENTIAL INFORMATION

The information in this study protocol is confidential. Any disclosure, copying or distribution of the information contained within is strictly prohibited without written consent from MonoSol Rx LLC.

APPENDIX C

Eating Assessment Tool² (EAT-10)

Please answer each of the ten questions listed below by **circling the appropriate number** that you feel best describes how you feel, with: 0= no problem at all; 4= severe problems.

Circle the appropriate response:

To what extent are the following scenarios problematic for you?	0= No Problem 4=Severe Problem				
	0	1	2	3	4
1. My swallowing problem has caused me to lose weight.	0	1	2	3	4
2. My swallowing problem interferes with my ability to go out for meals.	0	1	2	3	4
3. Swallowing liquid takes extra effort.	0	1	2	3	4
4. Swallowing solids takes extra effort.	0	1	2	3	4
5. Swallowing pills takes extra effort.	0	1	2	3	4
6. Swallowing is painful.	0	1	2	3	4
7. The pleasure of eating is affected by my swallowing.	0	1	2	3	4
8. When I swallow food sticks in my throat.	0	1	2	3	4
9. I cough when I eat.	0	1	2	3	4
10. Swallowing is stressful.	0	1	2	3	4
Total EAT-10					

² Belafsky PC, Mouadeb DA, Rees CJ, Pryor JC, Postma GN, Allen J, and Leonard RJ. Validity and reliability of the Eating Assessment Tool (EAT-10). Ann Otol Rhinol Laryngol 117: 919-924, 2008.

CONFIDENTIAL INFORMATION

The information in this study protocol is confidential. Any disclosure, copying or distribution of the information contained within is strictly prohibited without written consent from MonoSol Rx LLC.

APPENDIX D

Functional Oral Intake Scale (FOIS)

Functional Oral Intake Scale¹

TUBE DEPENDENT (levels 1-3)

- 1 No oral intake
- 2 Tube dependent with minimal/inconsistent oral intake
- 3 Tube supplements with consistent oral intake

TOTAL ORAL INTAKE (levels 4-7)

- 4 Total oral intake of a single consistency
- 5 Total oral intake of multiple consistencies requiring special preparation
- 6 Total oral intake with no special preparation, but must avoid specific foods or liquid items
- 7 Total oral intake with no restrictions

¹ Crary MA, Carnaby-Mann GD, Groher ME. Initial psychometric assessment of a functional oral intake scale for dysphagia in stroke patients. *Arch Phys Med Rehabil* 2005; 86:1516-1520.

CONFIDENTIAL INFORMATION

The information in this study protocol is confidential. Any disclosure, copying or distribution of the information contained within is strictly prohibited without written consent from MonoSol Rx LLC.

6.5.5 ALS Functional Rating Scale – Revised (ALSFRS-R).....	14
6.5.6 Functional Oral Intake Scale – FOIS	14
6.5.7 Eating Assessment Tool 10 – (EAT-10).....	15
6.5.8 Statistical Analyses	15
6.6 Changes to Methods Planned in the Protocol	16
7. REFERENCES.....	17

LIST OF ABBREVIATIONS AND DEFINITION OF TERMS

AE	Adverse Event
ALS	Amyotrophic Lateral Sclerosis
ALSFRS-R	Amyotrophic Lateral Sclerosis Functional Rating Scale-Revised
BMI	Body Mass Index
BP	Blood Pressure
CRF	Case Report Form
CSR	Clinical Study Report
EAT	Eating Assessment Tool
FDA	Food and Drug Administration
FOIS	Functional Oral Intake Scale
H	Above Normal Range
HR	Heart Rate
ICF	Informed Consent Form
L	Below Normal Range
Max	Maximum (equivalent to Max.)
MedDRA[®]	Medical Dictionary For Regulatory Activities
Mg	Milligram
Min	Minimum (equivalent to Min.)
N	Number of observations
PAS	Penetration Aspiration Scale
PT	MedDRA [®] Preferred Term
ROSF	Riluzole Oral Soluble Film
RR	Respiratory Rate
SAE	Serious Adverse Event
SAP	Statistical Analysis Plan
SAS[®]	Statistical Analysis System
SD	Standard Deviation
SOC	MedDRA [®] System Organ Class
SOP	Standard Operating Procedure
TEAE	Treatment-Emergent Adverse Event
VFSS	Videofluoroscopic Swallowing Study
WHO DD	World Health Organization Drug Dictionary

1. INTRODUCTION

This statistical analysis plan (SAP) is intended to give a detailed description of the summaries and the analyses that will be generated for the present study by inVentiv Health Clinical. Analyses specified in this plan are based on Protocol 17MO1R-0012 Version 2.0, Amendment I, dated 18 October 2017. Safety and tolerability analyses will be described.

The original plan has changed as described below. Further details are documented in the remainder of this document. These changes will also be described in the clinical study report (CSR).

Top-line clinical results from the Videofluoroscopic Swallowing Study (VFSS) for the first 7 completed patients were presented to the Food and Drug Administration (FDA) on Sept 10 2018. At that time, two additional patients had been enrolled but had not yet undergone the VFSS. On Sept 12 2018, the FDA agreed with the Sponsor that due to the lack of any signal of detrimental effect on VFSS after one dose of study drug, the study would be terminated after the completion of 9 patients (the seven completed by Sept 10 and the two additional patients in screening at that time). In addition to the lack of signal of any harmful effect, the Agency and the Sponsor took into account the difficulty and hardship involved for these disabled patients in participating in the study, the potential risks of participation (including possible reaction to barium, potential for aspiration, and exposure to radiation), and the fact that the participating patients would derive no direct benefit for participation.

When applicable, all methodology and related processes will be conducted according to Standard Operating Procedures (SOPs) of InVentiv Health Clinical.

2. STUDY OBJECTIVE

The objective is to evaluate the effect, if any, of a single 50 mg dose of Riluzole Oral Soluble Film (ROSF) on swallowing safety in individuals with amyotrophic lateral sclerosis.

3. STUDY DESIGN

3.1 General Design

This is a single site, phase 2, single dose, open-label safety study to evaluate the effect of Riluzole Oral Soluble Film (ROSF) on swallowing safety in individuals with Amyotrophic Lateral Sclerosis (ALS). The original plan called for approximately 30 subjects with ALS to be enrolled, with a goal of 25 completed subjects after allowance for dropouts. These subjects were to undergo a clinical evaluation including the validated Amyotrophic Lateral Sclerosis Functional Rating Scale-Revised (ALSFRS-R). Swallowing safety will be assessed using the gold standard Videofluoroscopic Swallowing Study (VFSS) to afford direct visualization of the swallowing process and any episodes of penetration or aspiration will be quantified using the validated Penetration Aspiration Scale (PAS). Subjects will undergo a standardized protocol that includes 11 bolus stimuli presentations of different liquid and food materials to test the swallow across a continuum of textures and materials. Immediately following this, subjects will be given a single dose of ROSF 50 mg, placed on the median lingual sulcus of the dorsum of the tongue. Three minutes after the administration of ROSF, the identical standardized VFSS protocol will be re-administered to allow a comparison of swallowing safety (using the PAS scale) pre vs. post ROSF administration.

The study visit duration is expected to be approximately 30 days from time of screening to completion of study.

3.2 Treatment description

A single dose of 50 mg Riluzole Oral Soluble Film (ROSF) will be administered to the subject, placed on the median lingual sulcus of the dorsum of the tongue. The treatment administered in this study is presented in Table 3-1

Table 3-1 Treatment Description

Treatment	Description
Riluzole 50 mg Oral Soluble Film	1 x 50 mg Riluzole Oral Soluble Film

This is an open-label study and neither subjects nor clinic staff will be blinded.

4. SCHEDULE OF ACTIVITIES

Evaluation	Screening	Visit 1
Written Informed Consent	X	
Inclusion/Exclusion Review	X	X ^a
Documentation of Disease	X	
Record/Review Concomitant Medications	X	X ^a
Medical History/ Demographics	X	
Height and Weight	X	
Vital Signs – HR, BP, RR		X ^b
Vital Signs – HR, BP, RR and temperature	X	X ^a
Comprehensive Physical Exam	X	
Brief Physical Exam		X ^b
Neurological Examination	X	
Brief Neurological Exam		X ^b
Eating Assessment Tool-10 (EAT-10)	X	X ^a
Functional Oral Intake Scale (FOIS)	X	X ^a
ALS Functional Rating Scale - Revised (ALSFRS-R)	X	X ^a
Oral Examination	X	X ^c
VFSS 1 - Penetration-Aspiration Scale (pre-dose)		X
VFSS 2 - Penetration-Aspiration Scale (post-dose)		X
Clinical laboratory evaluation(s) (hematology, chemistry, urinalysis) ^d	X	X ^b
Urine Pregnancy Test (females of childbearing potential)	X	X ^a
Adverse Event	X	X ^c
Dispense Study Drug (one dose)		X

^aBefore VFSS 1 procedure

^bAfter VFSS 2 procedure

^cBoth – before VFSS 1 procedure and after VFSS 2 procedure

^dSee [Section 6.5.4 Laboratory Parameters](#)

5. ANALYSIS POPULATION

The analysis of safety parameters will be based on the safety population detailed in Section [5.1](#) below.

5.1 Safety Population

The safety population is defined as the group of subjects who receive the study medication.

6. STATISTICAL METHODOLOGY

6.1 Statistical and Analytical Issues

6.1.1 Statistical Methods

Percentages and Decimal Places

If not otherwise specified, the following rules are applied, with the exception of listings:

- Percentages will be presented to 1 decimal point.
- Percentages equal to 0 or 100 will be presented as such without a decimal point.
- Minimum and maximum will be presented with the same precision as the original values and, mean, standard deviation, and median will be presented with one more decimal place than the original values.

Software to be used for Analysis

The inferential statistical analyses, the safety data tables and listings will be created using SAS[®], software version 9.4 or higher.

6.1.2 Handling of Dropouts and Missing Data

Missing values will not be imputed. The shifts required for the shift tables will already be included in the ADaM dataset.

6.1.3 Pooling of Investigative Sites

Pooling of investigative sites is not applicable for this study.

6.2 Determination of Sample Size

The original protocol specified that approximately thirty (30) subjects with ALS would be recruited to obtain a final sample size of at least 25 completed. As previously noted, the Sponsor and FDA have agreed to terminate the study with a completed sample size of 9 subjects.

6.3 Subject Characteristics

6.3.1 Subject Disposition

Subject disposition will be summarized as number and percentage of subjects in the treatment group for the below listed categories.

- Screened and screen failure subjects
- Enrolled and not enrolled subjects
- Dosed and not dosed subjects
- Number of subjects completed the study
- Number of subjects discontinued with reason

Subject disposition information will be listed. In addition, subjects who did not complete the VFSS will also be presented in this listing, including early termination reason and date and time of discontinuation.

For subjects enrolled, not enrolled and screen failures, the percentage denominator will be the number of screened subjects. For all other calculations, the percentage denominator will be the number of subjects dosed (safety population).

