The identical VFSS standardized bolus protocol exam will be performed provided that the subject did not demonstrate frank, gross and observable silent aspiration during VFSS 1-PAS and provided that the subject's PAS score in baseline test is 7 or below. VFSS will be performed using a Phillips BV Endura fluoroscopic C-arm unit (GE OEC 8800 Digital Mobile C-Arm system type 718074) that is housed within the PI's laboratory and used exclusively for research purposes. Fluoroscopic data will be captured in high resolution at 30 frames per second and in the lateral field of view using a TIMS Dicom (Version 3.2, TIMS Medical, TM, Chelmsford, MA).

The identical standard patient safety bail out criterion will be enforced in VFSS 2. This includes cessation of the specific testing phase on the third episode of frank aspiration or residue greater than 75% of either vallecular or pyriform housing that is unable to be cleared by the patient with prompting and strategies. Once the study is completed, recordings will be saved and digitally backed up for subsequent analyses of the PAS. Although this study is specifically investigating swallowing safety, this bailout criterion will still allow the study of up to three potential episodes of aspiration so that assessing impact on swallowing safety is still feasible while maintaining patient safety.

Missed Visit 1: When a subject fails to appear for scheduled Visit 1, the site will contact the subject. The site will stress the importance of the evaluation and reschedule within the 28-day window if possible.

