6.5.8 Statistical Analyses

The primary objective is to assess the effect of the ROSF formulation, if any, of a single 50 mg dose of ROSF on swallowing safety in subjects with ALS. The analyses will be descriptive only, and not hypothesis-testing.

The PAS scores obtained in swallow tests during VFSS 1-PAS (before ROSF) and VFSS 2-PAS (after ROSF) will be compared within each subject and across subjects.

Swallowing Evaluation Results:

There is considerable discussion in the literature regarding the psychometric properties and optimal/correct ways to analyze PAS scores (an 8-point ordinal scale, where higher scores indicate lower function, measured individually for 11 swallowing trials). There is no method universally accepted as best due to the psychometric and clinical characteristics of the PAS. The three methods described below will be used to present the results of this study. This approach was determined *post hoc*, at the time of examining results for the first seven patients.

“Single worst score” method:

A number of publications use the single worst score on any swallowing trial as an indicator of PAS swallowing function. Results presented will include the number/percentage of patients who stay the same, increase or decrease (and by how many points).

“Sum of scores” method:

The sum of 11 PAS scores will be used. Results presented will include the number/percentage of patients who stay the same, increase or decrease sum (and by how much).

“Steele 4-category” method:

Steele and associates (Dysphagia 2017) propose categorization of single worst PAS score into 4 categories. Steele A includes scores 1, 2, 4; Steele B includes 3, 5, 6; Steele C includes a score

of 7 and Steele D includes a worst score of 8. Results presented will include the number/percentage of patients who stay the same, increase or decrease (and by how much).

Interim Analyses:

An unofficial interim analysis was performed after 7 patients had completed the study. As previously mentioned, these results were discussed with the FDA and they agreed with the Sponsor that the study should be terminated after the two additional patients who had been screened but not yet completed were evaluated with the VFSS.

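### SAP 6.3.1 divides the dosed, not dosed, completed and discontinued rows by subjects dosed, and SAP 6.5.8 names no denominator for the PAS change percentages

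*SAP*

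**What the plan says.** SAP 6.3.1 asks for the number and percentage of subjects in a list of disposition categories. Besides the screening and enrolment counts, the list includes "Dosed and not dosed subjects", "Number of subjects completed the study" and subjects discontinued with a reason. Two sentences set the denominators. The first is "For subjects enrolled, not enrolled and screen failures, the percentage denominator will be the number of screened subjects". The second is "For all other calculations, the percentage denominator will be the number of subjects dosed (safety population". SAP 5.1 defines the safety population as "the group of subjects who receive the study medication".

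For the PAS, SAP 6.5.8 describes three descriptive summaries. For each of them, "Results presented will include the number/percentage of patients who stay the same, increase or decrease". No denominator is given. The safety population is the only population the SAP defines (SAP 5), PAS is listed among the safety data (SAP 6.5), and missing values are not imputed (SAP 6.1.2).

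In Protocol 10.2.2.1 the film is given directly after VFSS 1, with no stated condition on the VFSS 1 result. VFSS 2 is conditional: among other things, it requires that the "PAS score in baseline test is 7 or below".

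**The concern.** A disposition table should account for everyone who entered the study. Its denominator must therefore contain each subject who can appear in a numerator. Subjects dosed cannot serve for a row that counts subjects not dosed, nor for discontinuations that include people who stopped before the dose. The protocol foresees that group: sections 10.2.3, 10.2.4, 10.2.5 and 10.3.7 all provide for subjects who stop between VFSS 1 and dosing.

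The PAS summaries matter more, because SAP 6.5.8 drops hypothesis testing and these percentages now carry the primary objective. A change category exists only for a subject with both studies. A subject who is dosed but has no VFSS 2 belongs to the safety population and has no category. The SAP does not say whether that subject counts in the denominator. Such a subject may well be one who swallowed unsafely at VFSS 1, so the handling should be visible.

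**Working it through.** The SAP prints no disposition or PAS percentage, so there is no planned figure to reproduce. The check applies the stated rule to possible counts.

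**Inputs**

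- Completed subjects: 9 (SAP 6.2). I take completion to mean that both VFSS 1 and VFSS 2 were done; the SAP does not define it.
- a = subjects dosed without VFSS 2. Not given; assumed 0 to 2.
- b = subjects enrolled but not dosed. Not given; assumed 0 to 2.
- Dosed D = 9 + a. Enrolled E = D + b. Discontinued = a + b, if those who stop before dosing are counted.

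**Disposition**

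Under SAP 6.3.1: dosed = D/D, not dosed = b/D, completed = 9/D, discontinued = (a + b)/D. On an enrolled base, the same numerators are divided by E. Each cell below shows the SAP rule, then the enrolled base, in percent.

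| a | b | Dosed | Not dosed | Completed | Discontinued |
|---|---|---|---|---|---|
| 0 | 0 | 100 / 100 | 0 / 0 | 100 / 100 | 0 / 0 |
| 0 | 1 | 100 / 90.0 | 11.1 / 10.0 | 100 / 90.0 | 11.1 / 10.0 |
| 0 | 2 | 100 / 81.8 | 22.2 / 18.2 | 100 / 81.8 | 22.2 / 18.2 |
| 1 | 0 | 100 / 100 | 0 / 0 | 90.0 / 90.0 | 10.0 / 10.0 |
| 1 | 1 | 100 / 90.9 | 10.0 / 9.1 | 90.0 / 81.8 | 20.0 / 18.2 |
| 2 | 2 | 100 / 84.6 | 18.2 / 15.4 | 81.8 / 69.2 | 36.4 / 30.8 |

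- Dosed is 100% in every row under the SAP rule, so it carries no information.
- Dosed plus not dosed equals E/D. For a = 0, b = 1 this is 10/9 = 111.1%; for a = 0, b = 2 it is 11/9 = 122.2%.
- Completed plus discontinued also equals E/D, so it too exceeds 100% once b is above 0.
- Completion is overstated only when b is above 0. Over the assumed ranges the largest gap is 100 − 81.8 = 18.2 points (a = 0, b = 2).

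**PAS worsening**

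Let w of the 9 paired subjects worsen. The paired base gives w/9. A dosed base gives w/(9 + a), which is smaller by the factor 9/(9 + a).

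| a | Factor | w = 1: dosed / paired base | w = 3: dosed / paired base |
|---|---|---|---|
| 0 | 1.00 | 11.1 / 11.1 | 33.3 / 33.3 |
| 1 | 0.90 | 10.0 / 11.1 | 30.0 / 33.3 |
| 2 | 0.82 | 9.1 / 11.1 | 27.3 / 33.3 |

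This reduction arises only if dosed subjects without VFSS 2 are kept in the denominator.

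**The case against.** The strongest defence is that little may turn on this. The study stops at 9 completed subjects, counts are shown beside every percentage, and SAP 6.3.1 adds that "subjects who did not complete the VFSS will also be presented in this listing", with the reason and time of stopping. No passage reports an enrolled subject who was not dosed or a dosed subject without VFSS 2. All of that stands. It limits the harm, and it rules out any claim that loss before dosing is hidden. It does not make not dosed over dosed a valid proportion.

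Three stronger readings are tempting, and the documents support none of them.

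- A reader might infer that the sentence governs every percentage in the SAP. It closes the disposition section and most naturally covers the remaining rows of that table. SAP 6.3.3 names the safety population again for demographics, which would hardly be needed under a document-wide rule, and a dosed denominator is ordinary there.
- A reader might infer that PAS worsening is diluted as planned. SAP 6.5.8 names no denominator. Without imputation, a subject lacking VFSS 2 has no change category, so a paired-only base is equally open. The table shells are in a separate document (SAP 6.5) that may settle it.
- A reader might apply the 20% loss in Protocol 13.5.3 to dosing and obtain 6 not dosed out of 30. That figure is an expected loss of VFSS 2, and Protocol 10.2.2.1 does not make the dose depend on the VFSS 1 result. It is not a rate of subjects left undosed.

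**Conclusion.** The denominator rule for the dosed, not dosed, completed and discontinued rows of SAP 6.3.1 is wrong as written, and this does not depend on the data. Its numerical effect does. With 9 completers it is zero when every enrolled subject is dosed. With one subject enrolled but not dosed and none dosed without VFSS 2, completion prints as 100% against 90.0% of enrolled.

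The PAS point is weaker and should be stated as such: the denominator is unspecified and dilution is possible, not shown. For one worsened subject among 9 pairs, the difference is 1.1 percentage points with one dosed subject lacking VFSS 2 and 2.0 points with two. These sizes rest on 9 paired subjects and on assumed counts of 0 to 2 that the documents do not give. This is a minor defect in a descriptive plan, but it should be corrected because the remedy is simple and one of the tables concerns the main result.

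**What to change.** - In SAP 6.3.1, make subjects enrolled the denominator for dosed, not dosed, completed and discontinued, and restrict the not dosed row to enrolled subjects. Say what counts as enrolled, since the SAP Introduction describes the same two patients both as enrolled and as still in screening.
- In SAP 6.5.8, state that the same, increase and decrease percentages use subjects with both VFSS 1 and VFSS 2. Show the number dosed without VFSS 2 beside them. If the table shells already set a denominator, bring the two into line.

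The cost is a few sentences in the SAP and an edit to the table shells. Trial conduct and data collection do not change.
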